#### Methods:

We established a statistical analysis plan for transparent reporting of data analysis regarding the OPtriAL study. For this study, patients undergoing thoracoscopic anatomical lung resection are randomized into one of three arms: thoracic epidural analgesia, continuous paravertebral block or single-shot intercostal nerve block. Co-primary outcomes are: a) proportion of pain scores  $\geq$  4 as assessed with the numerical rating scale during postoperative day 0 until postoperative day 2 and b) quality of recovery, measured with the quality of recovery-15 questionnaire on postoperative days 1 and 2. In order to be non-inferior, the upper margin of the 98.65% one-sided confidence interval of the difference in mean proportions of pain scores  $\geq$  4 between the continuous paravertebral block and single-shot intercostal nerve block, both separately compared with the thoracic epidural analgesia, may not exceed 17.5% (predefined non-inferiority margin). Intention-to-treat and perprotocol analyses should both indicate non-inferiority to implement the intervention techniques as relevant alternatives to thoracic epidural analgesia. We expect a counterbalancing gain in quality of

recovery, which will be tested for superiority. Secondary outcomes such as length of stay, complications and patient mobility will also be tested for superiority.

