Non-inferiority for pain is obtained only if the upper limit of the 98.65% one-sided confidence interval (CI) of the differences of mean proportion of NRS  $\geq$ 4 between the PVB versus TEA and ICNB versus TEA remains below the predetermined absolute margin of 17.5% in the intention-to-treat (ITT) analysis as well as in the per-protocol (PP) analysis. This non-inferiority margin is based on data from a previous pilot study, in which the proportion of pain scores  $\geq$  4 in a group of patients receiving TEA was 17.57% (SD 19.57) and in patients receiving continuous locoregional analgesia 21.21% (SD 23.33). Since the baseline of 17.57% of moments of pain in the control group is low, we accept an absolute margin of 17.5% from a clinical point of view. This margin of non-inferiority, accepting more moments of pain in the intervention techniques as compared to the control group, is justifiable in combination with superiority regarding QoR. Superiority regarding QoR is defined as a significantly higher mean score during POD 1 and POD 2 (p < 0.027) in the ITT analysis. Taking the mean QoR score during POD 1 and POD 2 is a simplifying improvement of the original superiority definition in the published study protocol (1) without affecting the sample size calculation.

Secondary outcomes are: 1) pain scores during rest and mobilization at the recovery room, in the evening of the day of operation, and in the morning, afternoon and evening on POD 1 until POD 3, and at 2-3 weeks follow-up; 2) proportion of NRS scores ≥4 during mobilization during POD 0 until 2; 3) QoR-15 at POD 0, POD 3 and 2-3 weeks follow-up; 4) cumulative use of opioids and analgesics at POD 0 until 3 and the plain use of opioids at 2-3 weeks follow-up; 5) postoperative complications until POD 30; 6) hospitalisation; 7) patient satisfaction at POD 0 until 3; 8) time to removal of the chest tube; 9) time of an indwelling urinary catheter; 10) degree of mobility at POD 0 until 3 and 11) cost-effectiveness analysis (separate analysis).

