#### Protocol violation, adherence and deviation

Protocol violation is defined as non-adherence to the eligibility criteria, randomization process and study procedures, dictating that all patients should participate voluntarily and undergo an anatomical lung resection by VATS and one of the analgesic techniques (TEA, PVB or ICNB).

Protocol adherence defines that control patients should proceed to PVB catheter placement in case TEA catheter placement was unsuccessful; in case PVB too was unsuccessful, then ICNB should be done. Participants receiving TEA or PVB should have a provisional stop of the continuous analgesia at POD 2 and patients receiving TEA should have opioids administered through the epidural continuous mixture. Accidental luxation of the TEA or PVB catheter after surgery will not be seen as nonadherence.

Although the use of ERATS guidelines for enhanced postoperative recovery were advised by the protocol, it is expected that the level of implementation of each aspect of ERATS differs per hospital, for example the strict use of dexamethasone and 5-HT3 receptor antagonists. In addition, the availability of specific local anaesthetics (e.g. bupivacaine or ropivacaine) may vary and induce small between-hospital differences. To ensure equal distribution of small differences in ERATS aspects, we used treatment centre as stratification factor. Incomplete primary or secondary endpoints are considered a protocol deviation and are handled as missing data.

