#### Quality of recovery

QoR will be measured with the QoR-15 questionnaire at POD 1 and 2, and reported as the mean of these two values (Figure 2C). This outcome will be expressed as a discrete variable (minimum 0, maximum 150). Comparisons to test superiority will be made for the TEA versus PVB group and the TEA versus ICNB group. Superiority in terms of QoR is defined as a statistically significant higher mean score (p<0.027).

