#### Patient replacement and missing data

In the sample size calculation, we have considered 12.6% extra inclusions due to drop-outs after conversions to thoracotomy (late exclusion). Since this percentage is appropriately represented by data from the Dutch Clinical Audit database from 2017, we do not expect further patient

replacement. Clinical data management is performed by independent professional data managers from the Dutch Comprehensive Cancer Centre. Once inclusions are complete, careful inspection of the data will take place. The mechanism causing data to be missing, whether it is (completely) at random or not at random, will guide the study group to apply analytical methods to amend missing data.

The incidence of missing data is partially limited by study design where minimum numbers of measurements suffice to generate an outcome value. For our non-inferiority research question regarding pain, complete cases include patients with at least 3 NRS measurements during POD 0 until 2 or a LOS  $\leq$  2 days, to allow detection of curvilinear pain patterns over time for reliable imputation. The cut-off for LOS  $\leq$  2 days is established due to the expectation that patients who have been discharged from the hospital have a NRS score  $\leq$  4 (standard of care). For our superiority question regarding QoR, complete cases include patients with at least one QoR-score during POD 0 until 2.

In case of remaining patients with lacking outcome data below 5% of the study size (14), the baseline Table 1 will be reproduced for patients intended to be included in the analysis as complete cases and added to the supplementary material (15). Imbalances in covariate distributions across groups derived from observed SMDs in this table, will be assessed from a clinical perspective for potential bias in prognosis and adjusted for in a primary analysis based on complete cases.

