# Appendix A. Overview statistical test per outcome

Outcome	Planned statistical test to compare
	randomization groups (each intervention versus
	control)
Baseline characteristics	None*
Primary outcome	
% NRS ≥ 4 POD 0-2 (at rest)	Non-inferiority, upper limit 98.6% CI <17.5%
Mean QoR-15 POD 1-2	Unpaired t-test or Mann-Whitney U-test
Secondary outcomes	
% NRS $\geq$ 4 POD 0-2 (mobilization)	Unpaired t-test or Mann-Whitney U-test
% NRS $\geq$ 4 baseline, POD 0-3 and follow-up (at rest)	Linear mixed model
% NRS $\geq$ 4 baseline, POD 0-3 and follow-up	Linear mixed model
(mobilization)	
QoR-15 at baseline, POD 0-3 and follow-up	Linear mixed model
Cumulative use of analgesics POD 0-3	Unpaired t-test or Mann-Whitney U-test
Cumulative use of opioids POD 0-3	Unpaired t-test or Mann-Whitney U-test
Cumulative use of analgesics (including opioids) at follow-up	Unpaired t-test or Mann-Whitney U-test
Postoperative complications	Mantel-Haenszel chi-squared test or Fisher's
	exact test
Length of hospitalization	Mann-Whitney U-test
Patient satisfaction	Mantel-Haenszel chi-squared test or Fisher's
	exact test
Presence of chest drain	Unpaired t-test or Mann-Whitney U-test
Presence of urinary catheter	Unpaired t-test or Mann-Whitney U-test
Degree of mobility	Mantel-Haenszel chi-squared test or Fisher's exact test

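### The complete-case rule for QoR accepts a POD 0 score that is not part of the POD 1–2 endpoint, and the rule for pain accepts a short stay with no score at all (minor)

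*SAP*

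**What the plan says.** **QoR endpoint.** The abstract's Methods section describes the second co-primary outcome as "measured with the quality of recovery-15 questionnaire on postoperative days 1 and 2". The Quality of recovery section says "QoR will be measured with the QoR-15 questionnaire at POD 1 and 2, and reported as the mean of these two values", and Appendix A lists the outcome as "Mean QoR-15 POD 1-2". The Summary of the study protocol places the other time points among the secondary outcomes: "QoR-15 at POD 0, POD 3 and 2-3 weeks follow-up".

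**QoR complete cases.** Patient replacement and missing data says: "For our superiority question regarding QoR, complete cases include patients with at least one QoR-score during POD 0 until 2". The same paragraph opens by saying that minimum numbers of measurements are enough to give an outcome value. The section on protocol violation, adherence and deviation says: "Incomplete primary or secondary endpoints are considered a protocol deviation and are handled as missing data".

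**Pain.** The Summary of the study protocol defines the outcome as the number of NRS scores of 4 or more divided by the number of scores obtained from POD 0 to POD 2, at most 8 per patient. Scores below 4 are acceptable and scores of 4 or more are not. In the missing-data section a pain case is complete with at least 3 scores, or with a length of stay (LOS) of at most 2 days. The purpose given is "to allow detection of curvilinear pain patterns over time for reliable imputation". The LOS cut-off is justified by the expectation that "patients who have been discharged from the hospital have a NRS score" of 4 or lower.

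**The concern.** The missing-data section bases the primary analysis on complete cases. Its definition of complete therefore decides who is in that analysis, and who counts as lacking outcome data against the 5% threshold.

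For QoR the window is one day too wide. It admits a patient for whom nothing that enters the endpoint was observed, and no section says what value that patient receives. The analyst would have to choose, in an open-label trial and after data collection, between dropping the patient and using a score from a secondary time point.

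For pain, the LOS route has no minimum number of scores, so it can admit a patient whose outcome cannot be calculated. The reason given for that route also uses a cut-off that differs from the endpoint's by one scale point.

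**Working it through.** **1. QoR: the rules side by side**

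| QoR scores present | Missing-data section | Endpoint components observed | Deviation section, read literally |
|---|---|---|---|
| POD 1 and POD 2 | complete | 2 of 2 | complete |
| only one of POD 1 and POD 2 | complete | 1 of 2 | missing |
| POD 0 only | complete | 0 of 2 | missing |
| none in POD 0–2 | lacking outcome data | 0 of 2 | missing |

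The third row is the error. A POD 0 score cannot produce a POD 1–2 mean, although the paragraph says that its minimum suffices to produce an outcome value. Taken at its word, that sentence leaves the POD 0 score as the only value available.

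The second row shows a related gap. One of the two scores is meant to be enough, but the SAP does not say that this score then stands as the endpoint value, and the deviation section read literally would call it missing.

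**2. QoR: effect on the 5% count**

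Let m be the number of patients with no QoR score in POD 0–2, and k the number with a POD 0 score only. The SAP counts m; the number without any endpoint component is m + k.

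- With study size 450: 0.05 × 450 = 22.5, so the threshold is reached at 23 patients.
- With study size after the assumed 12.6% drop-out: 450 × (1 − 0.126) ≈ 393, and 0.05 × 393 = 19.65, so it is reached at 20 patients.

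Taking 450, the trial falls on the wrong side only if m ≤ 22 while m + k ≥ 23. Neither m nor k is in the SAP. The primary analysis is complete-case on both sides of 5%. At or above it, the SAP adds a study of missing-data patterns and, depending on the mechanism, supportive imputation and weighting or exploratory subgroup analyses. Only these additions are at stake.

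**3. Pain: the LOS route**

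Proportion = (scores of 4 or more) / (scores obtained).

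- No score obtained: 0/0, undefined, yet complete if LOS is at most 2 days.
- One score obtained: 0/1 = 0% or 1/1 = 100%. This is coarse but defined.

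One obtained score is therefore the least that makes the endpoint calculable.

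**4. Pain: the cut-off**

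The expectation for discharged patients is NRS at or below 4; the endpoint counts NRS at or above 4. A score of exactly 4 satisfies both, so the expectation as worded does not imply the absence of an endpoint event.

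**The case against.** **The QoR consequence may be nominal.** No section gives a POD 0-only patient a value, so a t-test or Mann-Whitney test would in practice leave that patient out. This largely stands. A reader might infer biased QoR results or lost power, but any such figure needs an assumed share of POD 0-only patients and an assumed substitution of the POD 0 score, and the SAP states neither. What remains is a rule that is wrong as written, an undercount of missing outcomes, and an open choice for the analyst.

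**The deviation section proves too much.** If every incomplete endpoint is missing, a patient with only one of the two scores is missing too. This is fair, and it is why changing the window alone is not enough.

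**The LOS route is a deliberate alternative.** It has its own rationale: early discharge should not by itself make a patient missing. This stands for every patient with at least one score. A reader might want the 3-score minimum applied here as well. The SAP does not support that as a correction. The proportion is defined from one score, and the stricter rule would exclude patients on a post-randomisation event that the Background section suggests may be more frequent with the locoregional techniques.

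A reader might also infer that a patient with a two-day stay and fewer than 3 scores must have missed several in-hospital assessments. That depends on reading days as nights. The Length of Hospitalization section uses whole nights, while the missing-data rule and Table 3 use days, so the inference is not secure.

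**The figure of 4 is only an expectation.** It is not a scoring rule, and the endpoint definition governs. This is correct, so the mismatch is an editorial matter.

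**Conclusion.** The QoR rule should be corrected. It contradicts the endpoint definition in three other sections and in Appendix A, and nothing elsewhere in the SAP resolves it. The pain part is smaller: an undefined value in what is probably a rare case, and a mismatch of one scale point in a rationale.

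The size is unknown. The only count of missing data in the SAP is from the interim look at pain in the TEA arm: 4 of 75 patients, or 4/75 = 5.3%. It concerns pain, covers one arm and is not split by cause, so it says nothing about POD 0-only QoR patients or short-stay patients without scores.

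No change in either co-primary conclusion is shown. A reader might try to count how many wrong pain proportions would bring the confidence bound to 17.5%. The SAP offers no basis for such errors, and dividing the remaining distance by the shift per patient would ignore the larger SD that extreme values bring.

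The verdict rests on reading the LOS clause as a separate route to completeness, which its wording and its own justification support. Severity: minor.

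**What to change.** In Patient replacement and missing data:

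1. **QoR window.** Require at least one score on POD 1 or POD 2, and count POD 0-only patients as lacking outcome data.
2. **QoR value.** State that when only one of the two scores is present, that score is the endpoint value. Amend the sentence on incomplete endpoints in the protocol deviation section so that it does not class these patients as missing.
3. **Pain, LOS route.** Require at least one obtained NRS score. A patient with none counts as lacking outcome data.
4. **Pain, cut-off and denominator.** Word the expected post-discharge score as below 4, to match the endpoint's coding; this concerns the outcome definition only and implies no discharge rule. Keep the denominator as scores obtained, so that moments after discharge receive no value in the primary proportion.

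The cost is a few words in two sections, best settled before the outcome data are examined. A few more patients may be reported as missing, and their number should be given by arm. Endpoints, margin, significance levels and sample size are unchanged.

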#### Summary of the study protocol

The OPtriAL (Optimal postoperative Pain management After thoracoscopic Lung resection) is a threearm multicentre pragmatic randomized controlled trial comparing TEA, continuous PVB and single-

shot ICNB in adult patients undergoing thoracoscopic anatomical lung resection. The study comprises two co-primary outcomes with different designs: a non-inferiority design for the outcome 'pain' and a concomitant superiority design for the outcome 'quality of recovery'.

Adult patients (>18 years) referred for thoracoscopic anatomic lung resection (segmentectomy, (bi)lobectomy and pneumonectomy for either benign or malignant disease) are eligible for the trial. We exclude patients with a contraindication for one of the analgesic techniques, chronic use of opioids, a high probability of conversion to thoracotomy or in case of insufficient Dutch proficiency. Written informed consent is obtained from each participating patient before randomisation. Patients are randomized in a 1:1:1 ratio for one of the three analgesic techniques by a computerized database (Research Manager) with an unchangeable computer-generated number. Randomization is done in random block sizes of 6, 9 and 12. As anaesthesia and surgical protocols may slightly differ between hospitals, randomization is stratified by treatment centre. Blinding is unfeasible due to clear visible differences of the analgesic techniques and would potentially compromise the safety of the patient (analgesic catheter, indwelling urinary catheter, mobility with or without prerequisites).

The first co-primary outcome relates to pain and the second to QoR. Pain is measured with the numerical rating scale (NRS 0-10; 0=no pain, 10=worst imaginable pain). A NRS score <4 indicates acceptable pain and ≥4 indicates unacceptable pain as it implies the clinical need for additional analgesia. Therefore, our primary outcome 'pain' for non-inferiority is expressed as the proportion of postoperative NRS scores in rest ≥4, defined as the number of NRS ≥4 measurements divided by the total number of NRS measurements obtained from postoperative day (POD) 0 until POD 2. Each patient has a maximum of 8 measurements: at the recovery room, the evening of the day of the operation, and in the morning, afternoon and evening of POD 1 and 2. Superiority of the second coprimary outcome 'QoR' is measured with the QoR-15 questionnaire (lowest score of 0 and highest score of 150) at POD 1 and POD 2.

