The sample size calculation resulted in 450 patients in total (150 for each randomization group) to demonstrate non-inferiority regarding proportion of NRS measurements ≥4 (power 99%, one-sided Type 1 error of 0.0135) as well as superiority regarding QoR (power 90%, two-sided Type 1-error of 0.027), taking into account an assumed 12.6% drop-out for conversions to thoracotomy (in the Netherlands, data from the Dutch Lung Cancer Audit from 2017) and controlling for the family-wise

error rate associated with the comparison of the two experimental groups (PVB and ICNB) with the same control group TEA (1).

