#### Interim and final analysis

Since the point estimators regarding proportion of measurements with a NRS  $\geq$ 4, used in our sample size calculation for non-inferiority, were based on a small pilot study they may have limited reliability. We therefore established a Data Safety Monitoring Board (DSMB), including a methodologist, statistician and two clinical experts (anaesthesiologist and thoracic surgeon) to assess whether our study generates sufficient power to answer the research question. When 50% of the observations in the TEA group (control) were completed (n=75), the DSMB performed an interim analysis to evaluate the point estimator and variance of the proportion of NRS measurements ≥4 of the control group and advised whether adjustment of our sample size was necessary. The DSMB only had access to all patients who underwent TEA and could warn the research team of potential risk factors and suspension of inclusions. The interim analysis by the DSMB was performed in January 2023. Based on pain scores of 70 complete TEA patients (4 patients had missing data and 1 patient was treated as TEA but randomized for ICNB) in the ITT analysis, no changes in the sample size were required. The final analysis will be performed when all data of 450 patients is collected. No specific stopping rules apply since the OPtriAL has been classified as having negligible risk for study subjects. The SPIRIT flow diagram in Table 1 of the published protocol (1) demonstrates a complete overview of the schedule of assessments.

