In case of remaining patients with lacking outcome data at or above 5% of the study size, the same procedure will be followed including a reproduced baseline table. In addition, missing data patterns will be studied to assess the likelihood of data being missing (completely) at random. If data are likely to be missing completely at random, multiple imputation (e.g. K-nearest neighbour imputation; multiple imputation by chained equation) and inverse probability weighting will be applied with presumably prognostic co-variates to substantiate the findings of the primary analysis. If data are likely to be missing at random, exploratory subgroup analyses will be run to restrict the target population for implementation of study results to the subgroups of patients closest to the observed

effect estimate in the complete case analysis. Restriction on the generalizability of study results will be fully reported in the supplementary material and discussed in the manuscript.

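### The 5% missing-data trigger is a share of the whole three-arm study, so in the worst case almost 15% of one arm could lack a co-primary outcome with only a baseline-adjusted complete-case analysis specified

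*SAP*

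**What the plan says.** The SAP section on patient replacement and missing data has two branches, separated by one threshold.

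- **Lower branch:** "In case of remaining patients with lacking outcome data below 5% of the study size". Table 1 is reproduced for the complete cases. Imbalances seen there are judged clinically and "adjusted for in a primary analysis based on complete cases".
- **Upper branch:** "In case of remaining patients with lacking outcome data at or above 5% of the study size". The same steps apply, and then: "In addition, missing data patterns will be studied to assess the likelihood of data being missing (completely) at random". If the data look missing completely at random, multiple imputation and inverse probability weighting support the primary analysis. If they look missing at random, the plan names exploratory subgroup analyses only.

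The only study size that the SAP gives is 450, with 150 per arm (Summary of the study protocol; "Patients are randomized in a 1:1:1 ratio"). Neither branch has a criterion per arm, for a difference between arms, or per co-primary outcome.

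Every confirmatory test compares PVB or ICNB with TEA. Pain is tested against a 17.5-point margin with a one-sided 98.65% limit, and QoR for superiority at p < 0.027.

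**The concern.** Missingness biases a difference between two arms when it is uneven between them or related to the outcome. A threshold counted over three arms cannot see unevenness: a nearly complete arm offsets a gap in another. TEA enters both comparisons, so a gap there affects both.

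Uneven missingness is plausible. The trial is open-label, and its arms differ visibly in catheters and mobility. Below the threshold, the specified protection is adjustment for measured baseline imbalance. That does not address missingness related to the outcome itself.

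At stake is a non-inferiority or superiority conclusion drawn from complete cases, with no specified check on how far it depends on the absent patients.

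**Working it through.** **Inputs**
- Study size 450, 150 per arm; assumed late exclusion 12.6% (Summary of the study protocol).
- Pilot mean proportions of NRS ≥4: TEA 17.57 (SD 19.57), continuous locoregional analgesia 21.21 (SD 23.33). Difference 21.21 − 17.57 = 3.64 points.
- Margin 17.5 points; one-sided alpha 0.0135 (z = 2.21); QoR two-sided alpha 0.027, that is 1.35% in the favourable direction.

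**Evaluable patients.** 150 × (1 − 0.126) = 131 per arm, 393 in total. In reverse, 131/(1 − 0.126) = 150, which agrees with the SAP's arm size.

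**Largest count below the threshold**

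| Base for the 5% | 5% of base | Largest count below | All in one arm |
|---|---|---|---|
| 450 randomised | 22.5 | 22 | 22/150 = 14.7% |
| 393 evaluable | 19.65 | 19 | 19/131 = 14.5% |
| one arm of 150 | 7.5 | 7 | 7/150 = 4.7% |
| one arm of 131 | 6.55 | 6 | 6/131 = 4.6% |

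Spread evenly over the three arms, 22 missing patients are 4.9% of each.

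**Pain.** Error in the complete-case arm mean = fraction missing × gap between missing and observed patients (gap assumed). Headroom under the pilot figures = 17.5 − 3.64 = 13.86 points.

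| Assumed gap | Shift, 22/150 | Share of headroom | Shift, 7/150 |
|---|---|---|---|
| 20 points | 2.9 | 21% | 0.9 |
| 30 points | 4.4 | 32% | 1.4 |
| 40 points | 5.9 | 42% | 1.9 |

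Does this reverse the decision? Take 131 against 131 − 19 = 112 patients and an observed difference of 3.64.
- Pooled SD = √((19.57² + 23.33²)/2) = 21.53. SE = 21.53 × √(1/131 + 1/112) = 2.77. Expected upper limit = 3.64 + 2.21 × 2.77 = 9.8.
- With SD 23.33, SE = 3.00 and the limit is 10.3.
- Adding the largest shift, 5.9, gives 15.7 and 16.2. Both are below 17.5.

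**QoR.** The SAP gives no QoR SD, so the scale is SD units. Suppose the true difference is zero and 19 of 131 are missing in the experimental arm, with means 0.5 or 1 SD below the observed patients (assumed).
- SE = √(1/131 + 1/112) = 0.129 SD.
- Gap 0.5 SD: shift 19/131 × 0.5 = 0.073 SD, or 0.56 SE. P(Z > 2.21 − 0.56) = 5.0%.
- Gap 1 SD: shift 0.145 SD, or 1.13 SE. P(Z > 2.21 − 1.13) = 14%.
- Without missingness the figure is 1.35%.

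**The case against.** **It is a corner case.** The 14.7% needs every missing patient to be in one arm. If one arm had twice the rate of each of the other two (an assumption), 11 of 22 would fall there: 7.3%, with a shift of 1.5 points at a 20-point gap and 2.9 at 40. The completeness rules are also lenient: three NRS readings or a short stay for pain, and a single score for QoR. This stands, and the figures above are upper limits. A trigger is nevertheless meant to catch the bad case.

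**The plan has other safeguards.** The same section promises inspection of the data and says that the missingness mechanism will guide the choice of method, whatever the amount missing. Exclusions are reported with reasons. The mixed model for rest pain uses all available observations, and QoR-15 over time is also modelled. So it would be wrong to say that nothing is done below 5%. But the general promise names no method, and the mixed models are secondary analyses that do not estimate the two co-primary contrasts.

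**Pain non-inferiority would probably survive.** Under the pilot figures it would. A reader might infer that the pooled threshold could produce a false non-inferiority finding; the SAP's own planning values do not support that at gaps up to 40 points. Two limits apply. The pilot comparator was a continuous technique, not single-shot ICNB, and the SAP itself calls the pilot estimates possibly unreliable.

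**The interim count.** The SAP reports for TEA: "4 patients had missing data and 1 patient was treated as TEA but randomized for ICNB". A reader might infer that the control arm is already above 5% (4/75 = 5.3%, or 4/74 = 5.4%) and that the arms differ. The text supports neither. It does not say that missing was defined there as in the missing-data section, or that the data were lost for good, and it gives no count for the other arms. If 5.4% held everywhere, about 24 of 450 would be missing and the pooled trigger would fire.

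**A pooled 5% rule is a cited convention.** The SAP gives a reference for 5%. The point here is not that value but its use across three arms when the tests are pairwise.

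**Conclusion.** The point holds as a weakness in how the trigger is built, and it should be fixed before analysis. A share of the whole study does not match pairwise tests. In the worst case it leaves 14.5% to 14.7% of one arm without a co-primary outcome, with no imputation, weighting or pattern study specified.

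For pain, the worst case uses 21% to 42% of the assumed headroom at gaps of 20 to 40 points. It would not by itself be expected to reverse non-inferiority if the pilot difference and SDs hold. QoR superiority is the more exposed outcome, because any shift acts directly on the test: 1.35% becomes about 5% to 14%. These results rest on all missing patients being in one arm and on the assumed gaps. The documents give no evidence on how large such gaps would be, or that missingness in fact differs between arms.

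**What to change.** In the section on patient replacement and missing data:

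1. Apply the 5% trigger to each arm and to each co-primary outcome separately. It would then fire at 8 of 150 or 7 of 131 patients.
2. When any arm reaches it, run multiple imputation for every comparison that includes that arm, under missing at random as well. Moving the trigger alone is not enough: the upper branch now names imputation and weighting only when data look missing completely at random, and only subgroup analyses under missing at random.
3. In the same case, add a delta-shift (tipping-point) analysis. Change the missing patients' values in one arm until the 17.5-point non-inferiority conclusion changes, and likewise until the QoR superiority conclusion changes. Report the shift needed. This is the part that tests missingness related to the outcome.

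The cost is SAP wording and somewhat more analysis, including one sensitivity analysis that is not now planned. No new data and no change to the design or sample size are needed.
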